6.8.2.2 Analyses

Summary statistics will be provided for all secondary PD endpoints variables, by time point, and individual data will be listed.

The variables' extent of aggregation, absolute PRU, IPA, and FPA will be analyzed similarly to the longitudinal analysis described for the primary PD endpoint in Section 6.8.1.2, and will use the same factors.

A logistics regression model will be used to assess the treatment effect relative to placebo of each ACT-246475 dose on subject platelet aggregation status 8 hours after study drug administration. The factor considered in addition to the treatment group, will include injection site (abdomen, thigh), PRU level at randomization (stratification levels), age (continuous), and sex (male, female) as fixed factors. The model will also include (treatment \times injection site) as an interaction term to assess consistency of treatment effect across injection sites.

Proportion of subject by platelet aggregation status 8 hours after study drug administration will be plotted as bar charts. Additional graphs will be provided by injection site.

6.8.2.3 Supportive/sensitivity analyses

Not applicable.

6.8.2.4 Subgroup analyses

Descriptive summaries will be provided for each secondary PD endpoints using the same sub-groups as defined in Section 6.8.2.4.

Descriptive statistics will also be provided for secondary PD endpoints by injection site sub-group.

6.8.3 Handling of missing data

Subjects for whom determination of the PD response is not possible will not be included in the computation of response rate for the main analysis, however they will be counted as non-responders in the sensitivity analysis.

No other imputations are planned.

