10.3.2.2 Handling of missing data

Subjects for whom determination of the response is not possible will be counted as non-responders in the main analysis; no other imputation will be considered.

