6.8.1 Primary pharmacodynamic endpoint

6.8.1.1 Variable

The primary PD endpoint is the *PD response* that is defined for each subject as a PRU < 100 starting 30 min after injection and lasting for at least 3 h, as measured via VerifyNow®.

The primary PD variable is the platelet reactivity as measured by VerifyNow® at each time point [see tables of assessments in the protocol: table 2 and table 3].

The analysis variable of the PD response is defined as follows for a given subject:

IF maximum of (PRU_{30m}, PRU_{1h}, PRU_{2h}, PRU_{4h}) < 100

AND (no more than 1 intermediate value (PRU_{1h} or PRU_{2h}) missing)

THEN PD response = YES

ELSE PD response = NO

Where PRU_{30m}, PRU_{1h}, PRU_{2h}, and PRU_{4h} refer to PRU measured by VerifyNow® at 30 minutes, 1, 2 and 4 hours after study drug administration. Time is based on planned time point and not on the actual collection time.

Supportive primary PD endpoint estimands

To assess robustness of results, two additional PD endpoints (estimands) will be defined for sensitivity analysis. The first endpoint, noted PD response[#], will be based on the same

algorithm as described above but using the actual collection time to define the following time windows:

Table 4 Time windows definitions

Collection time point (nominal) (time post study drug administration)	Time from PRU _{30m} (assessment of response, i.e., PRU < 100)	Time windows (~ 5% margin) (min. from study drug administration)
15 minutes	-	14 to 16
30 minutes	0	28 to 32
1 hour	30 minutes	57 to 63
2 hours	1.5 hours	114 to 126
3.5 hours*	3 hours	199 to 221
4 hours	3.5 hours	228 to 252
8 hours	7.5 hours	456 to 504
24 hours	23.5 hours	1368 to 1512

* no blood sample is taken at that time point, therefore no PRU value reported.
PRU, P2Y₁₂ reaction units.

The second endpoint, in the event of frequently missing PRU_{1h} or PRU_{2h} values, $\geq 10\%$ missing values overall, noted PD response*, will consider only the 30 minutes and 4 hours post study drug administration time points:

*IF maximum of (PRU_{30m}, PRU_{4h}) < 100
AND none of those values is missing
THEN PD response* = YES
ELSE PD response* = NO*

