6.8.1.3 Supportive/sensitivity analyses

The same analysis as described in the main analysis section will be performed on the additional PD response endpoints: PD response[#] and PD response^{*}.

The main analysis will be repeated on the PPS, if the size of the PPS is less than 10% compared to the size of the FAS.

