8.1.2 Descriptive statistics

Descriptive statistics will be provided by treatment group (and all pooled groups for study subjects analyses) depending on the nature of the criteria:

Quantitative:

Number of observed values, number of missing values, mean, SD, minimum and maximum, median, 1st and 3rd quartiles.

Qualitative:

Number of observed values, number of missing values, number and percentage of subjects per level/category.

Unless otherwise specified in the table shells, the percentage calculation will not consider missing values in denominators.

The number of missing values is displayed only if > 0 . For continuous variables, it is displayed after the number of non-missing observations, for categorical variables after the last category (no percentage reported).

Listings are grouped by treatment arm (same order as in tables headers, if applicable, screening failures are listed last), subject identification number and assessment date as applicable.

Raw data listings, if required, are based on datasets as received. All data collected are displayed, including unscheduled visits (if any).

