11.3 Clarifications concerning endpoint definitions and related variables or statistical methods

Not applicable.

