Appendix B Protocol deviation list

The actual list of protocol deviation leading to exclusion from analysis set will be updated prior to study closure if required.

Table below provides the reason considered for excluding subjects from analysis set.

Table 7 Definition of exclusions from analysis sets

Analysis set	Reason for exclusion from analysis set	Programming conditions
Screened analysis set	Informed consent not initially obtained for the study	DV.DVREFID = IPD1D1
Randomized analysis set	Subject does not have a randomization number	Not in DS.RANDNO
Full analysis set	Subject did not get study treatment	EX.EXDOSE not >0
Safety set	Subject did not get study treatment	EX.EXDOSE not >0
Per-protocol set	Previous exposure to investigational drug	DV.DVREFID = IPD2A6
	Subject with platelet disorders at Screening	DV.DVREFID = IPD2A9
	Initiation or change in dose of oral P2Y12 during study	DV.DVREFID = IPD2D1
	Incorrect administration of study drug	DV.DVREFID = IPD2E1 or IPD3C1
	Deviation from study drug preparation instructions	DV.DVREFID = IPD2E2
	Incorrect blood sampling for platelet assays	DV.DVREFID = IPD2F2
	Background oral antiplatelet therapy not stable for 1 month prior to randomization	DV.DVREFID = IPD2A1
	Subject does not have stable coronary artery disease	DV.DVREFID = IPD2A3
	At least one post-dose VerifyNow® blood sample not evaluable (excluding the 24 h post dose)	at least one missing LB.LBSTRESN where LB.LBTESTCD= "P2Y12RU" and LB.LBTPT in (15 MIN POST-DOSE, 30 MIN POST-DOSE, 1 HOUR POST-DOSE, 2 HOURS POST-DOSE, 4 HOURS POST-DOSE, 8 HOURS POST-DOSE)
	Subject taking OATP1B1 and/or OATP1B3 inhibitor (systemic route) at Screening	DV.DVREFID = IPD2A7
PK analysis set	Subject has no plasma concentration measurement after administration of study treatment	all PC.PCSTRESC = « » when PC.PCTPT not PRE-DOSE

ICF, informed consent form; OATP, organic anion transporting polypeptide; PK, pharmacokinetic(s).

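### Protocol and SAP give opposite main-analysis rules for subjects whose PD response cannot be determined; the SAP also contradicts itself and does not list the change

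*SAP*

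**What the plan says.** - **Protocol 10.3.2.2:** "Subjects for whom determination of the response is not possible will be counted as non-responders in the main analysis". It allows no other imputation.
- **Protocol 10.3.1:** no imputation in the main PD analysis; imputation is possible in sensitivity or exploratory analyses.
- **SAP 6.8.3:** the same subjects "will not be included in the computation of response rate for the main analysis". They become non-responders only in the sensitivity analysis.
- **SAP 6.8.1.1:** the algorithm gives YES if the maximum of the 30 min, 1 h, 2 h and 4 h PRU values is below 100 and a missing-value condition holds, "AND (no more than 1 intermediate value" (1 h or 2 h). Everything else falls to "ELSE PD response = NO".
- **SAP 6.8.1.3:** "The same analysis as described in the main analysis section will be performed on the additional PD response endpoints", namely PD response# and PD response*, plus a repeat on the per-protocol set under a size condition.
- **SAP Appendix B, Table 7:** the per-protocol set drops anyone with at least one post-dose VerifyNow "blood sample not evaluable (excluding the 24 h post dose" sample).
- **SAP 8.1.2:** unless the table shells say otherwise, "the percentage calculation will not consider missing values in denominators".
- **SAP section 11:** 11.1 lists one change, to the 8 h PRU variable. Section 11.3, headed "Clarifications concerning endpoint definitions and related variables or statistical methods", and section 11.4 are marked not applicable.

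**The concern.** The same subjects in the same main analysis are failures under one document and absent from the denominator under the other. Within the SAP, a programmer working from 6.8.1.1 and one working from 6.8.3 can produce different primary results. Neither document defines when a response is undeterminable.

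The study is positive only if at least one dose beats placebo and then also exceeds a 70% response rate. That second test compares one arm with a fixed number, so every undetermined subject counted as a failure pulls the arm towards 70% with no offsetting shift in a comparator. If the rule is still open when the data are seen, the result could turn on which section is followed.

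**Working it through.** **Reproducing the plan's sample size.** Protocol 10.5 uses 70% against 85%, two-sided alpha 0.025 and power 0.90. The one-sample z formula with null variance in the alpha term gives

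n = (2.241·√(0.70·0.30) + 1.282·√(0.85·0.15))² / 0.15² = 97.98, i.e. 98.

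Then 98 × 1.10 = 107.8, i.e. 108 per arm, and 3 × 108 = 324. The plan's figures reproduce. Protocol 10.3.2.1 and SAP 6.8.1.2 plan the test as one-sided 0.025, so results are given at that level, with the sizing level (one-sided 0.0125) in brackets.

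**When the two rules disagree.** z = (p̂ − 0.70)/√(0.21/n), one-sided, 108 dosed in the arm:

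| Responders | Undetermined | Excluded | Non-responder |
|---|---|---|---|
| 85 | 8 | 85/100, p=0.0005, pass | 85/108, p=0.024, pass |
| 84 | 9 | 84/99, p=0.0006, pass | 84/108, p=0.039, fail |
| 84 | 3 | 84/105, p=0.013, pass | 84/108, p=0.039, fail |

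With about 85% responders among determined subjects the rules split from 9 undetermined; with 80% they split from 3.

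**Power per dose, reading A** (85% applies to evaluable subjects; undetermined share m, unrelated to response). Power = Φ[((p₁ − 0.70) − z_α·√(0.21/n)) / √(p₁(1 − p₁)/n)].

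- Excluded: n = 108(1 − m), p₁ = 0.85.
- Non-responder: n = 108, p₁ = 0.85(1 − m).

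For example, at m = 5% under the non-responder rule, p₁ = 0.8075 and (0.1075 − 0.0864)/0.0379 = 0.556, giving 71%.

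| m | Excluded | Non-responder |
|---|---|---|
| 0% | 97% [93%] | 97% [93%] |
| 2% | 96% [93%] | 90% [83%] |
| 5% | 96% [92%] | 71% [59%] |
| 10% | 95% [90%] | 30% [20%] |

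Exact binomial rejection probabilities of the z-test under the non-responder rule at 0.025 (85 of 108 needed) are 97, 92, 75 and 34%. A simulation of the full two-step procedure (400,000 runs, placebo 50% among evaluable subjects) gave 97.1, 91.7, 75.1 and 34.2%, so the placebo step costs almost nothing.

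**At least one of two doses**, both truly at 85%, non-responder rule, 1 − (1 − power)²: above 99, 99, 92 and 51%. With one dose at 85% and the other at 75% (assumed, simulated): 98, 93, 76 and 35%.

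**Reading B** (85% already counts undetermined subjects as failures): n = 108, p₁ = 0.85, power 97% [93%], no loss. Protocol 10.5 supports reading A, because it inflates 98 evaluable subjects to 108. Protocol 10.3.2 and SAP 6.8.1.2 support reading B, because they set 85% for enrolled or randomized subjects.

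**Is the protocol rule kept anywhere by name?** PD response# redefines timing, and PD response* uses only 30 min and 4 h and applies only if at least 10% of 1 h or 2 h values are missing. The per-protocol repeat removes the subjects in question. SAP 6.8.1.3 therefore names no analysis of the primary PD response on the FAS with undetermined subjects as failures.

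**A separate gap in the algorithm.** The missing-value condition covers only 1 h and 2 h. If the maximum is taken over observed values, a subject without a 30 min or 4 h value could be scored YES. PD response* requires both values. None of the figures above depend on this.

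**The case against.** The best defence of the SAP is that the protocol is itself divided. Section 10.3.1 rules out imputation in the main PD analysis and permits it in sensitivity analyses, which is the order SAP 6.8.3 follows, and sizing on evaluable subjects also fits exclusion. This may explain the SAP wording. It does not settle the matter: 10.3.2.2 is the specific provision for this endpoint and bars any imputation other than the non-responder rule. It does mean that the protocol needs correcting too.

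Other points on that side:

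- Protocol section 10 lets deviations be justified in the SAP or the study report, and 6.8.3 states its rule openly. So non-declaration is shown for SAP section 11 only. A later report cannot fix the rule before unblinding.
- PD response# and PD response* also end in NO and could be read as the non-responder sensitivity analysis. They are different endpoints.
- The denominator default in SAP 8.1.2 is descriptive and yields to table shells that are not in the documents. It adds little weight.
- Few subjects may be undetermined. The FAS holds only dosed subjects, the endpoint is complete 4 h after a single on-site injection, and one missing 1 h or 2 h value is tolerated. The plan's 10% also covers drop-outs, so the 10% row is an upper bound. At 2% the non-responder rule still gives 90%.
- The power table assumes that missingness is unrelated to response. If any observed PRU of 100 or more makes a subject a determined failure, the undetermined group is richer in would-be responders. In the extreme, at 10% undetermined, power is about 87% under exclusion (p₁ = 0.75/0.90) and 19% under the non-responder rule (p₁ = 0.75). Exclusion is then not neutral either.

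These points limit the size of the effect and leave the contradiction in place.

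**Conclusion.** The concern holds and must be fixed: the plan is wrong as written. The two documents state opposite main-analysis rules, the SAP algorithm conflicts with SAP 6.8.3, and SAP section 11 does not record the change. The same data can pass the test against 70% under one rule and fail under the other with as few as 3 undetermined subjects of 108.

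The power loss is conditional. It rests on reading A, on 108 dosed per arm, on missingness unrelated to response, and on the undetermined share in the FAS, which the documents do not give. To keep 90% per dose under the non-responder rule, that share may be at most 2.1% at one-sided 0.025 (0.7% at 0.0125). Under reading B there is no loss. The need for one rule does not depend on these assumptions.

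**What to change.** Before unblinding, adopt one rule in both documents and code it in SAP 6.8.1.1:

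1. Any observed PRU of 100 or more at 30 min, 1 h, 2 h or 4 h gives NO.
2. YES requires non-missing 30 min and 4 h values, at most one missing intermediate value, and all observed values below 100.
3. Anyone else is undetermined: a non-responder in the main analysis with the FAS as denominator, and excluded in a sensitivity analysis named in 6.8.1.3.

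Reword SAP 6.8.3 to match, state that the 8.1.2 denominator default does not apply to this endpoint, and reconcile protocol 10.3.1 with 10.3.2.2. If the sponsor prefers exclusion as the main rule, amend the algorithm accordingly and declare and justify the change in SAP 11.1. Either way, report the number undetermined per arm. In protocol 10.5, say whether 85% refers to evaluable or all dosed subjects, and restate per-arm power under the chosen rule over 0–10% undetermined.

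The cost is wording, a few lines of derivation code and, under reading A, a less favourable stated power. No extra patients are needed to disclose this. Restoring 90% per arm under the non-responder rule would be a different decision: at one-sided 0.025, 108 per arm suffices at 2% undetermined, but 5% needs 171 and 10% needs 492 (129, 204 and 584 at one-sided 0.0125).

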6.9 Analysis of pharmacokinetic variables

The PK variables will be summarized and listed using the PK set.

The plasma PK parameters of ACT-246475 will be derived by non-compartmental analysis of the plasma concentration-time profiles. PK endpoints include: maximum observed plasma concentration (C_{max}), time to reach C_{max} (t_{max}), and the area under the plasma concentration-time curve from time zero to 24 h time point (AUC_{0-24h} ; study drug administration to 24 h time point post administration).

Log-transformed value of C_{max} and AUC_{0-24h} , will be used in the analysis.

The PK parameters (linear and log-transformed ones) will be summarized by dose group using descriptive statistics, i.e., arithmetic mean, SD, geometric mean, minimum, median, maximum, standard error, and 2-sided 95% CI of the means and coefficient of variation in %. Graphical representation of PK results over time (scheduled time point) will be provided using box-whisker plots. For t_{max} , the geometric mean and its 95% CI will not be calculated.

PK variables summary will be provided by dose, injection site, PRU category used for stratification, and by gender.

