2.2 Other objectives

The other objectives of this study, following a single s.c. administration of ACT-246475, are:

- To assess the PK of ACT-246475.
- To assess the impact of the injection site location (thigh vs abdomen) on the PK and PD of ACT-246475.
- To investigate the impact of concomitant drug use, age, sex, and other covariates on the PK and PD of ACT-246475.
- To investigate the safety and tolerability of ACT-246475.

[figure not shown]

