3 OVERALL STUDY DESIGN AND PLAN

3.1 Study design

This is a prospective, multi-national, multi-center, double-blind, randomized, placebo-controlled, parallel-group, Phase 2, exploratory study of a single s.c. administration of ACT-246475, at 2 different dose levels, in subjects with stable CAD receiving conventional background therapy (e.g., acetylsalicylic acid, P2Y₁₂ receptor antagonists, etc.).

Approximately 324 adult subjects with stable CAD will be randomized into 1 of the 8 combinations of the treatment, dose, and injection site using a 2:2:2:2:1:1:1:1 ratio as described in [Figure 1](#).

Figure 1 Randomization scheme

Each subject will receive a single s.c. administration of either 8 mg ACT-246475, 16 mg ACT-246475 or matching placebo, either in the thigh or in the abdomen.

Treatment group allocation will be stratified based on baseline platelet reactivity value (expressed as P2Y₁₂ reaction units [PRU]) measured on Day 1 by the VerifyNow® assay before ACT-246475 injection, considering the 3 following categories: high reactivity (PRU > 250), medium reactivity (150 ≤ PRU ≤ 250), and low reactivity (PRU < 150).

No interim analysis is planned for this study.

The study will be conducted at approximately 20 sites and in 5–10 countries (recruitment will be competitive across sites). The list of sites including the name and title of the investigators who are responsible for conducting the trial, and the address and telephone numbers of the trial sites will be filed in the Trial Master File (TMF).

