10.2.4 Pharmacokinetic and pharmacodynamic variables

10.2.4.1 Pharmacokinetic variables

Plasma concentrations per time point will be listed by treatment arm and subject, and summarized by time point and dose group using arithmetic and geometric mean,

minimum, median, maximum, standard deviation (SD), standard error (SE), and 2-sided 95% confidence interval (CI) of the means and coefficient of variation (CV) in %.

PK parameters will be derived using non-compartmental methods:

- C_{max} , t_{max} , and AUC_{0-24h} will be listed by dose group and subject and will be summarized by dose group.
- C_{max} , t_{max}^* , and AUC_{0-24h} will be summarized with arithmetic mean, geometric mean, minimum, median, maximum, SD, SE, CV (%), and 95% CI of the arithmetic and geometric means.
(* For t_{max} the geometric mean and its 95% CI will not be calculated).
- Log-transformed C_{max} and AUC_{0-24h} values will be summarized with mean and SD of the logs.

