3.3 Other objectives

The other objectives of this study, following a single s.c. administration of ACT-246475, are:

- To assess the pharmacokinetics (PK) of ACT-246475.
- To assess the impact of the injection site location (thigh vs abdomen) on the PK and pharmacodynamics (PD) of ACT-246475.
- To investigate the impact of concomitant drug use, age, sex, and other covariates on the PK and PD of ACT-246475.
- To investigate the safety and tolerability of ACT-246475.

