8.1.1 Treatment groups

The study included the following 8 *randomization groups* corresponding to the combination of the four study treatment groups (i.e., ACT-246475 8 mg, ACT-246475 16 mg, and their matching placebos) and two injection sites (thigh and abdomen).

The main purpose of this randomization strategy was to balance treatment as well as site of injection assignment. For the analysis, the study treatment arms will consist of the treatment arms: *Placebo*, *ACT-246475 8 mg*, and *ACT-246475 16 mg*. The placebo treatment arm combines the two placebo dose-matching groups.

All analyses, unless stated otherwise, will be reported by those 3 treatment arms, and in this order.

In all Tables, Figures and Listings, treatment groups will be labeled using treatment label [last column of [Table 6](#)].

Table 6 Randomization groups and treatment group labels

Randomization groups		Treatment groups (labels for outputs)
Treatment	Injection site	
ACT-246475 8 mg	Thigh	ACT-246475 8 mg
ACT-246475 8 mg	Abdomen	
ACT-246475 16 mg	Thigh	ACT-246475 16 mg
ACT-246475 16 mg	Abdomen	
Placebo matching ACT-246475 8 mg	Thigh	Placebo
Placebo matching ACT-246475 8 mg	Abdomen	
Placebo matching ACT-246475 16 mg	Thigh	
Placebo matching ACT-246475 16 mg	Abdomen	

Some analyses may require displaying some of the following groups: *Screened failure* subjects group, *Total randomized* (i.e., any subject who has been assigned a study treatment), *Total ACT-246475* group (i.e., subjects randomized to either ACT-246475 8 or 16 mg arms), and *Total* (i.e., all subjects screened).

The order of the treatment group in the statistical report, would then be: Screened failures, ACT-246475 8 mg, ACT-246475 16 mg, Total randomized, Total ACT-246475, and Total.

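### Injection site is randomised and its effect on PK is a stated objective, but SAP 6.9 plans only descriptive summaries and no thigh/abdomen contrast

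*SAP*

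**What the plan says.** **Objective.** Protocol 2.2 includes "To assess the impact of the injection site location (thigh vs abdomen) on the PK and PD of ACT-246475", and SAP 3.3 repeats it. Protocol 1.4 also names the two injection sites among the factors whose effect on PK will be assessed.

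**Design.** Protocol 3.1 has subjects "randomized into 1 of the 8 combinations of the treatment, dose, and injection site using a 2:2:2:2:1:1:1:1 ratio". SAP 8.1.1 explains: "The main purpose of this randomization strategy was to balance treatment as well as site of injection assignment".

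**PK analysis.** Protocol 10.2.4.1 says Cmax, tmax and AUC0-24h "will be listed by dose group and subject and will be summarized by dose group"; site is not mentioned there. SAP 6.9 states "Log-transformed value of C_{max} and AUC_{0-24h} , will be used in the analysis", then specifies descriptive statistics by dose group, including "2-sided 95% CI of the means and coefficient of variation in" percent. It closes with "PK variables summary will be provided by dose, injection site, PRU category used for stratification, and by gender". It does not say whether site is crossed with dose, and it names no model, contrast or ratio. SAP 11.4 adds no analyses.

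**PD analysis.** The PRU mixed model (SAP 6.8.1.2) and the 8-hour platelet aggregation status model (SAP 6.8.2.2) both contain injection site and a treatment-by-site interaction.

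**The concern.** One objective covers PK and PD. The PD half gets models that estimate a site effect, while the PK half gets tables. Intervals for two group means are not an interval for their ratio, and a reader left to compare them by eye will tend to understate the evidence for a difference. The log transformation in SAP 6.9 suits a ratio analysis, but none is specified.

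At stake is how clearly the trial answers a question it randomised for. Protocol 1.1 says the product is being developed for self-injection, and Protocol 1.4 says the data are meant to inform dose selection in later trials. A site effect on exposure is therefore worth reporting as a pre-specified estimate with an interval.

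**Working it through.** **1. Subjects available (the plan's own figure).** The ratio 2:2:2:2:1:1:1:1 has 12 parts. 324 × 2/12 = 54 per active dose-by-site cell, and 324 × 1/12 = 27 per placebo cell. This matches the randomisation diagram in SAP Appendix A. Over both active doses, thigh versus abdomen is 108 versus 108. The sample size (Protocol 10.5) rests on the PD endpoint; nothing is sized for PK or for site.

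**2. What overlap of separate intervals amounts to.** Take two independent log means with equal standard error SE. Their 95% intervals just touch when the difference is 2 × 1.96 × SE. The standard error of the difference is √2 × SE, so z = 1.96 × √2 = 2.77 and the two-sided p is about 0.006. Overlap is thus a stricter criterion than a 5% test.

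**3. What happens if the site summary is not split by dose.** Protocol 1.3.2.3 reports dose-proportional exposure in healthy subjects. Taking 16 mg to give twice the exposure of 8 mg, mixing equal groups adds (ln 2)²/4 = 0.12 to the log-scale variance. The within-dose variance is ln(1 + CV²). The documents give no CV, so 30–60% is an assumption.
- CV 30%: variance 0.086; √((0.086 + 0.120)/0.086) = 1.55, so intervals are about 55% wider.
- CV 60%: variance 0.307; √((0.307 + 0.120)/0.307) = 1.18, so intervals are about 18% wider.

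A model with dose as a factor removes this variance.

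**4. Precision of a planned ratio.** Log-scale SD s = √ln(1 + CV²), which is 0.294 at CV 30% and 0.555 at CV 60%. The 95% CI around a true ratio of 1.00 is exp(± t × s × √(2/n)), with n per site and t on 106 df per dose or 213 df for both doses with dose and site in the model. Estimating the interaction as well costs one more degree of freedom, which is immaterial here.

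| Comparison | CV 30% | CV 60% |
|---|---|---|
| Both doses, dose-adjusted, 108 vs 108 | 0.92–1.08 | 0.86–1.16 |
| Per dose, 54 vs 54 | 0.89–1.12 | 0.81–1.24 |
| Both doses, 98 vs 98 | 0.92–1.09 | 0.86–1.17 |
| Per dose, 49 vs 49 | 0.89–1.13 | 0.80–1.25 |

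The last two rows use the 98 evaluable subjects per arm of Protocol 10.5 (49 per site), which reflects its allowance of about 10% drop-out or non-evaluable data.

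These rows show what the design can deliver. The difference between the pooled and per-dose rows is the gain from combining doses. It does not measure what is lost by reporting descriptively.

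**The case against.** The strongest reply is that the information is nearly there. Cmax and AUC0-24h are summarised on the log scale with means and standard errors. If those statistics are shown by site, the ratio is exp(mean log thigh − mean log abdomen), and its standard error is the root of the summed squares of the two standard errors. Because site is randomised, no adjustment is needed for an unbiased comparison. If the table is crossed with dose, the two dose-specific ratios can be combined by inverse variance. A reader might infer that the trial cannot say how large the site effect is; the documents do not support that. What stands is that such a calculation would be unplanned, with pooling and interval level left open.

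Nor can one say that the summaries fail to pool the doses. The SAP 6.9 sentence may mean separate one-way tables, where the site table covers both doses, or a crossed table. Step 3 applies only to the first reading.

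Descriptive reporting is also defensible for an item outside the primary objective in a study labelled exploratory, and SAP 6.9 already goes beyond the protocol by adding site. That limits the weight of the point. It does not explain why the same objective is modelled for PD and not for PK.

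Finally, SAP 12 refers to a separate list of outputs that is not available here. A ratio table in it cannot be excluded, but the SAP text specifies none.

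**Conclusion.** The point holds as a gap in estimation. The objective is stated, site is randomised within dose, and neither document plans a between-site PK estimate with an interval. Under the assumed CV of 30–60%, the design could give a dose-adjusted ratio with a 95% CI from about 0.92–1.08 to 0.86–1.16 with no extra subjects, slightly wider with about 10% non-evaluable data.

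A reader might go further and ask the trial to exclude a relevant site difference. The documents define no margin, equivalence range or hypothesis for exposure by site, so they support an estimate and not an equivalence claim. The primary analysis, sample size and success criterion are untouched. This is a worthwhile improvement of low severity.

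**What to change.** Add to SAP 6.9 a linear model on log Cmax and log AUC0-24h, in PK-set subjects who received ACT-246475 (placebo excluded), with dose, injection site and dose-by-site as factors. Report the thigh/abdomen geometric mean ratio with a pre-specified CI, both by dose and dose-adjusted. Use 95% to match the rest of the SAP, or 90% with a stated reason. Label it as estimation only, with no equivalence conclusion. In the same edit, state whether the descriptive site summary is crossed with dose.

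The cost is a sentence or two in the SAP and one small table from data already collected, with no added subjects, samples or visits.
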